5.0 Study design

This is a prospective, Phase 2, single center study in a total of 40 subjects with Neuroendocrine Tumors (NETs). Study participants will receive 68Ga-DOTATOC and undergo a PET/CT imaging study, to investigate its suitability as a PET imaging agent for NETs. The radiation (imaging) dose will be $111-185 \, \text{MBq} (3 - 5 \, \text{mCi}) \pm 25\%$. All doses after labeling will be presented in buffered solution for intravenous injection. Imaging will start 90 $\pm 30 \, \text{minutes}$ after injection.

About 40 patients with histologically and/or clinically confirmed and/or suspected NET are anticipated to be enrolled during 3 years from initiating the study.

Patients will be recruited at Montefiore Medical Park where there is a medical group specialised in the diagnosis and treatment of NETs. Each patient will undergo a screening visit within 14 days prior to receiving study medication.

The primary goal of the analysis is to estimate the diagnostic accuracy of 68Ga-DOTATOC PET-CT for detecting NET compared to conventional imaging techniques.

The patients will be followed up by a telephone call 24 hour after administration of test drug (⁶⁸Ga-DOTATOC) to assess if patients have experienced any adverse event. This information will be captured in the CRF for further assessment.

5.1 Image Acquisition:

5.1.1 PET imaging

⁶⁸Ga-DOTATOC PET images will be acquired 90 ±30 minutes after injection of 111–185 MBq (3-5 mCi) ±25% of ⁶⁸Ga-DOTATOC. Any adverse effects will be documented after the injection of ⁶⁸Ga-DOTATOC. Imaging will be performed with patients in supine position using the Philips Gemini TF time-of-flight (TOF) PET/CT scanner (Philips Medical Systems, Cleveland, Ohio) with a spatial resolution of 5 mm in the center of the field of view, with emission scan acquired for 1 min 40 sec. per frame in 3D acquisition mode. Proprietary vendor-provided software will be used for image reconstruction with LISTMODE OS-EM reconstruction algorithm (33 subsets, 3 iterations). The low-dose CT (LDCT) scan will be used for non-uniform attenuation correction. Both scatter and random corrections will be performed by embedded program provided by the vendor.

5.1.2 CT Scan

CT scan will be performed using the CT exposure factors for all examinations of 140 kVp and 80-100 mA in 0.8 s. With patient position maintained, a whole-body PET emission scan will be performed covering an area identical to that covered by CT; scans will be performed in 3-dimensional mode. All PET acquisitions will be carried out in 3-dimensional mode (5 min per bed position), in an approximately 40-min scanning time. PET images will be reconstructed using CT for attenuation correction and using ordered-subsets expectation maximization with 2 iterations and 24 subsets.

5.1.3 PET/CT Images

The images from ⁶⁸Ga-DOTATOC PET/CT will be reported by experienced nuclear medicine physicians. Areas of abnormal focal uptake will be documented. These areas of abnormal uptake will be compared with any prior cross-sectional imaging (CT or MRI) within 12 weeks to confirm the presence of lesions.

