5.2. Interpretation of Data

The number of lesions that could be identified clearly as single focus will be determined for each patient. To enable a methodic and consistent approach to lesion identification, we will create 3 categories of lesion sites: organs (Head and Neck, lungs, breast, liver, pancreas, gastrointestinal tract, kidney, spleen, and pelvis/ovaries), nodal regions (Axillary, thoracic, mesenteric, abdominal, and pelvic [excluding mesenteric], and inguinal regions), and musculoskeletal system (vertebrae, bony thorax, bony pelvis, and limb bones). Because of confluence and inability to clearly delineate single liver lesions in some cases, liver metastases will be classified as 1 organ metastasis, independent of the number of liver metastases present. Lymph nodes smaller than 1 cm on CT or MRI and showing marked avidity for ⁶⁸Ga-DOTATOC will be labeled as positive for

disease. In cases where images from ¹¹¹In-Octreotide are available for comparison, the same imaging parameters will be applied. The presence of lesions will be confirmed by cross-sectional imaging of all patients with CT or MRI. As there may be lesion/s that can show abnormal focal activity on Ga-68 PET images but not on morphologic images, such lesion/s will be considered positive NET.

Each scan (⁶⁸Ga-DOTATOC) will be read by two independent, board certified nuclear medicine physicians blinded to the results of other scan. A third independent nuclear medicine physician will then review both the results (independent reviews) and clinical information to reach to a consensus.

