5.4 Statistical Analysis

The primary goal of the analysis is to estimate the diagnostic accuracy of 68Ga-DOTATOC PET-CT for detecting NET compared to conventional imaging techniques. Analyses will be performed with both patient and lesion as the unit of observation. Since all patients are expected to have at least one NET lesion, only sensitivity can be estimated in the analysis by patient, whereas both sensitivity and specificity will be estimated in the lesion based analysis. We will compute the relevant proportions and corresponding 95% confidence intervals, with adjustment for correlated data from the same patient. Results from pathology reports available from previous biopsy or surgical specimens will be considered the gold standard. In the absence of pathology reports, initial and follow up diagnostic CT or MRI scan following nonsurgical therapy including chemotherapy will be considered the gold standard.

Kappa statistics will be computed and McNemar's test will be performed to compare the sensitivity and specificity between ⁶⁸Ga-DOTATOC PET-CT with SPECT and diagnostic CT for detecting NET. All analyses will be performed in SAS and p-values < 0.05 will be considered statistically significant.

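### Lesion confirmation is described only from PET to CT/MRI, with no CT/MRI result fixed before PET is known: the non-pathology reference is not independent of PET, and the CT comparator may not be

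*Combined protocol and SAP*

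**What the plan says.** Section 5.1.3 has nuclear medicine physicians document areas of abnormal focal uptake and continues: "These areas of abnormal uptake will be compared with any prior cross-sectional imaging (CT or MRI", within 12 weeks, the stated purpose being to confirm that lesions are present. No corresponding step is described for sites where PET is negative.

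Section 5.2 adds "The presence of lesions will be confirmed by cross-sectional imaging of all patients with CT or MRI". It also contains two rules by which PET sets disease status. For a focus seen on PET but not on morphologic images, "such lesion/s will be considered positive NET". And "Lymph nodes smaller than 1 cm on CT or MRI and showing marked avidity for" the tracer are labelled positive for disease.

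Blinding is described only for the 68Ga-DOTATOC scans, which are read by two independent "board certified nuclear medicine physicians blinded to the results of other scan". Then "A third independent nuclear medicine physician will then review both the results (independent reviews) and clinical information to reach to a consensus". No reader of the CT/MRI is named, and none is blinded to PET.

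Section 5.4 (Statistical Analysis) makes pathology from earlier specimens the gold standard and, where there is none, initial and follow-up diagnostic CT or MRI. In the same section "McNemar's test will be performed to compare the sensitivity and specificity between" PET-CT on one side and SPECT and diagnostic CT on the other. It does not say whether the CT result entered is the original report or a review made with PET in hand.

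Criterion 3.6 requires a CT or MRI of the tumour region or suspected area before dosing.

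**The concern.** A comparison of two imaging tests needs each result recorded without knowledge of the other, and a reference that neither test has shaped. Here the written order is PET first, then CT/MRI at the places PET has marked. A faint CT change that was not called originally may be called once PET points to it. It could then serve as confirmation of the PET finding and also be scored as a CT detection. In the other direction, a lesion visible on CT where PET is negative has no described route into the lesion list.

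The stake is the primary objective, accuracy relative to conventional imaging. Two analysts following the text could build different 2x2 tables from the same scans, depending on which CT result they used and how they searched PET-negative sites.

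The protocol's own literature shows that PET misses occur. In section 2.3, item 12 (46 patients), CT showed disease not detected on DOTATOC in 1 + 3 = 4 patients. In item 5, cross-sectional imaging identified 226 lesions and PET detected 168, so 226 − 168 = 58 were missed. Item 5 used a related tracer in patients with negative or equivocal scintigraphy, so its rate may not carry over.

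**Working it through.** **Plan figures.** Section 5.4 (Justification of Sample Size) gives 40 patients × 2 = 80 lesions, 60% positive, hence 48 positive and 32 negative. The half-width 1.96 × √(0.25/n) gives 14.1% for n = 48, 17.3% for n = 32 and 15.5% for n = 40. The stated 14%, 17% and 15% therefore reproduce approximately, with lesions treated as independent. They describe single proportions. The plan gives no figure for the PET-versus-CT difference.

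**PET-versus-CT difference.** The following are assumptions, not plan values: PET sensitivity s = 0.85; CT sensitivity t = 0.60, 0.70 or 0.80; independent errors; and u, the share of PET-positive lesions missed by CT that PET-guided review recovers. For scale, the 84-patient study in section 2.3, item 3, gives CT 41/(41 + 26) = 61% by patient.

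- Blinded read of all sites: gap = s − t. At t = 0.60 the discordant counts are 48 × 0.85 × 0.40 = 16.3 (PET+/CT−) and 48 × 0.15 × 0.60 = 4.3 (PET−/CT+), and (16.3 − 4.3)/48 = 25 points.
- Only PET-positive sites examined: PET scores 100% by construction, the PET−/CT+ cell is empty, and gap = (1 − t)(1 − u).
- All sites examined, with prompting at PET-positive ones: gap = s − t − u·s·(1 − t). At t = 0.60 and u = 0.5 this is 0.25 − 0.5 × 0.34 = 0.08.

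| CT sensitivity | Blinded, all sites | PET-positive sites only, u = 0 | PET-positive sites only, u = 0.5 | All sites, u = 0.5 |
|---|---|---|---|---|
| 60% | 25 | 40 | 20 | 8 |
| 70% | 15 | 30 | 15 | 2 |
| 80% | 5 | 20 | 10 | −4 |

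Entries are percentage points. Prompting alone shrinks the gap and restriction alone widens it. Together they can shrink it, leave it unchanged or widen it.

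**PET accuracy.** Let v be the fraction of PET-negative sites checked, with assumed sensitivity 85% and specificity 90%. Then TP = 40.8, FN = 7.2, TN = 28.8 and FP = 3.2. At v = 0.5, apparent sensitivity is 40.8/(40.8 + 3.6) = 91.9% and apparent specificity is 14.4/(14.4 + 3.2) = 81.8%. So incomplete checking raises sensitivity and lowers specificity.

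The PET-only rule in section 5.2 acts separately. If all 3.2 false positives are relabelled as NET and all sites are checked, specificity is 28.8/28.8 = 100% and sensitivity is (40.8 + 3.2)/(48 + 3.2) = 85.9%.

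**The case against.** The strongest reply is that section 5.1.3 describes how the PET/CT is reported and does not define the reference standard. Section 5.4 does that, and neither of its tiers is limited to PET-positive sites. Section 5.2 speaks of cross-sectional imaging of all patients. A planned specificity with about 32 negative lesions presupposes that some PET-negative sites are assessed. Pathology comes from earlier specimens, so a PET-guided look cannot shape it. The prior CT/MRI is acquired before dosing, and nothing says that a PET-informed re-read replaces its report.

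Most of this stands. A reader might infer that CT/MRI is examined at PET-positive sites only, or that the CT comparator is certainly contaminated. The documents say neither: the first is not written, and the second is a risk that comes from silence. Follow-up CT/MRI could also reveal some PET misses.

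A reader might also charge the PET-guided look with inflating specificity by 1/32, about 3 points, for each false positive it confirms. The PET-only rule already counts such a focus as NET whatever CT shows, so that gain belongs to the rule.

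The reply does not close the gap. All patients is not all sites, the 32 negative lesions come with no procedure for finding them, and no sentence says which CT result enters McNemar's test.

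**Conclusion.** The point holds as a gap in independence. The only confirmation procedure described runs from PET to CT/MRI, no CT/MRI result is fixed or blinded beforehand, and two rules in section 5.2 let PET define disease. The non-pathology reference is therefore not independent of PET, and the CT comparator may not be.

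No single direction of bias follows. A claim that the PET-versus-CT difference is pulled toward zero, or that it is inflated, goes beyond the documents. At assumed sensitivities of 85% and 60%, a true gap of 25 points could be reported as anything from 8 to 40, depending on choices the plan leaves open. These limits rest on independent errors and a 50% prompted recovery, and the upper limit on a complete restriction to PET-positive sites that the text does not state. They show how much is undetermined and do not predict the result.

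The point merits correction because the remedy is cheap and bears on the primary objective.

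**What to change.** Amend sections 5.1.3, 5.2 and 5.4 (Statistical Analysis) as follows.

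1. Define the CT/MRI comparator as the complete lesion list in the report issued before the 68Ga-DOTATOC scan. Enter it in the CRF by the section 5.2 site categories before the PET read is opened, including lesions at sites that later prove PET-negative. Do the same for SPECT where it exists; section 5.2 expects 111In-Octreotide images in some patients only. Where no written report exists, use a read blinded to PET.
2. Limit the paired comparison to site categories the prior scan covered. Criterion 3.6 requires only the tumour region or suspected area, so sites never imaged would otherwise be scored CT-negative, in favour of PET.
3. Put CT/MRI findings made only on PET-guided review in a separate category that is not CT-positive in McNemar's test. Take the CT status of small avid nodes from the pre-PET report as well.
4. In the primary accuracy analysis, count neither these findings nor PET-only foci as reference-positive unless pathology or follow-up CT/MRI supports them. This requires changing the PET-only rule in section 5.2; without that change, the other steps would leave PET-only foci labelled as NET. Report results with and without them.
5. Reconcile the 12-week window in section 5.1.3 with the 4-6 months in criterion 3.6, since an eligible scan may fall outside the confirmation window.

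The cost is CRF ordering and SAP wording. No extra imaging is needed, because criterion 3.6 already requires the prior scan. Fewer lesions will count as confirmed, and restricting the site categories removes some pairs, so the PET figures may be somewhat less favourable or less precise.

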5.2. Interpretation of Data

The number of lesions that could be identified clearly as single focus will be determined for each patient. To enable a methodic and consistent approach to lesion identification, we will create 3 categories of lesion sites: organs (Head and Neck, lungs, breast, liver, pancreas, gastrointestinal tract, kidney, spleen, and pelvis/ovaries), nodal regions (Axillary, thoracic, mesenteric, abdominal, and pelvic [excluding mesenteric], and inguinal regions), and musculoskeletal system (vertebrae, bony thorax, bony pelvis, and limb bones). Because of confluence and inability to clearly delineate single liver lesions in some cases, liver metastases will be classified as 1 organ metastasis, independent of the number of liver metastases present. Lymph nodes smaller than 1 cm on CT or MRI and showing marked avidity for ⁶⁸Ga-DOTATOC will be labeled as positive for

disease. In cases where images from ¹¹¹In-Octreotide are available for comparison, the same imaging parameters will be applied. The presence of lesions will be confirmed by cross-sectional imaging of all patients with CT or MRI. As there may be lesion/s that can show abnormal focal activity on Ga-68 PET images but not on morphologic images, such lesion/s will be considered positive NET.

Each scan (⁶⁸Ga-DOTATOC) will be read by two independent, board certified nuclear medicine physicians blinded to the results of other scan. A third independent nuclear medicine physician will then review both the results (independent reviews) and clinical information to reach to a consensus.

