3.0 Inclusion Criteria

- 3.1 Signed informed consent.
- 3.2 Patients of either gender, aged ≥18 years.
- 3.3 Karnofsky status ≥60.
- 3.4 Life expectancy of at least 12 weeks.
- 3.5 Histologically and/or clinically confirmed and/or suspicious of NET.
- 3.6 A diagnostic CT or MRI of the tumour region or suspected area within the previous 4-6 months prior to dosing day is available.
- 3.7 Recent Blood test results up to 4-6 weeks as follows:
 - 3.7.1 WBC: >2*109/L
 - 3.7.2 Haemoglobin: >8.0g/DI
 - 3.7.3 Platelets: >50x10⁹/L
 - 3.87.4 ALT, AST, AP: ≤5 times ULN
 - 3.7.5 Bilirubin: ≤3 times ULN
- 3.8 Serum creatinine: within normal range or <120µmol/L for patients aged 60 years or older.
- 3.9 Negative pregnancy test in women capable of child-bearing.

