5.4 Justification of Sample Size

We project that it will be feasible to recruit a total of 40 patients with histologically and/or clinically confirmed and/or suspected NET into the study. Each subject is expected to have on average 2 lesions and among the 80 total lesions; we project that 60% will be positive for NET. To evaluate the adequacy of the sample size (i.e., number of lesions), we computed the precision, as measured by the width of the 95% CI, with which the sensitivity and specificity of 68Ga-DOTATOC PET-CT scan can be estimated. The width of the 95% CI will be no greater than +/-14% for sensitivity and +/- 17% for specificity in the lesion-based analysis. For the patient-based analysis, the precision with which sensitivity can be estimated is +/- 15%.

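### The plan does not say whether section 5.2's rule on PET-only foci is a reading rule or a truth rule competing with section 5.4's gold standard, and lesion-level accuracy depends on the answer

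*Combined protocol and SAP*

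**What the plan says.** Two sections carry the number 5.4; below, 5.4 means Statistical Analysis unless the sample-size section is named.

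- **Section 5.2, Interpretation of Data.** The general rule is "The presence of lesions will be confirmed by cross-sectional imaging of all patients with CT or MRI". The next sentence deals with lesions that "can show abnormal focal activity on Ga-68 PET images but not on morphologic images, such lesion/s will be considered positive NET". A separate rule covers small nodes: "Lymph nodes smaller than 1 cm on CT or MRI and showing marked avidity for" the tracer are to be labelled as disease-positive.
- **Section 5.1.3.** Areas of abnormal uptake are compared with CT or MRI from the preceding 12 weeks, to confirm that a lesion is present.
- **Section 5.4.** The first tier is pathology: "Results from pathology reports available from previous biopsy or surgical specimens will be considered the gold standard". Where there is none, "initial and follow up diagnostic CT or MRI scan following nonsurgical therapy including chemotherapy will be considered the gold standard". PET has no role, there is no exception for PET-only foci, and 5.2 is not mentioned.
- **Use of the labels.** Section 5.4 estimates sensitivity by patient, and both sensitivity and specificity by lesion. It compares PET-CT with SPECT and diagnostic CT by McNemar's test.
- **Imaging available.** Section 3.0 requires "A diagnostic CT or MRI of the tumour region or suspected area within the previous 4-6 months prior to dosing day is available", whereas under 5.1.2 "a whole-body PET emission scan will be performed covering an area identical to that covered by CT". The only follow-up contact scheduled in section 5.0 is a telephone call at 24 hours to ask about adverse events.

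**The concern.** The main objective is accuracy compared with conventional imaging, and foci seen only on PET are exactly where the methods part. Sections 5.2 and 5.4 can give such a focus different labels, and no section says which prevails.

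- **If 5.2 sets truth,** the test under study helps to define disease. A PET-only focus without pathology becomes a PET true positive and a CT miss automatically.
- **If 5.4 alone sets truth,** the same focus is a PET false positive when follow-up CT/MRI stays negative, and CT is judged largely against itself. Without follow-up imaging the focus has no label at all. A focus outside the region covered by the diagnostic CT/MRI may not have an initial one either.

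Two analysts following the protocol faithfully could therefore report different lesion sensitivity, specificity and McNemar results from the same scans. If the choice is made after the scans are read, the results can steer it.

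**Working it through.** **Planned numbers.** The sample-size section expects 40 patients and 80 lesions, 60% of them positive: 0.60 × 80 = 48 positive and 32 negative. The stated precision is "The width of the 95% CI will be no greater than +/-14% for sensitivity and +/- 17% for specificity in the lesion-based analysis". The worst-case half-width is 1.96 × √(0.25/n): 14.1% for n = 48 and 17.3% for n = 32. The figures reproduce, so 48 and 32 are the intended denominators. They are half-widths at a proportion of 50% with independent lesions, so they are not a yardstick for the differences below.

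**Assumptions (not in the documents).** Let k be the number of PET-only foci without pathology that stay negative on CT/MRI. Place them among the 32 negatives, and let PET and CT agree and be correct on every other lesion. McNemar is exact and two-sided (the plan does not state sidedness).

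**Formulas.**
- PET specificity: (32 − k)/32 under 5.4; (32 − k)/(32 − k) = 100% under 5.2.
- CT sensitivity: 48/48 = 100% under 5.4; 48/(48 + k) under 5.2.
- McNemar with k discordant lesions against 0: p = 2 × 0.5^k. Under 5.4 this is a specificity result against PET; under 5.2 it is a sensitivity result for PET.

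| k | PET specificity, 5.4 | PET specificity, 5.2 | CT sensitivity, 5.4 | CT sensitivity, 5.2 | McNemar p |
|---|---|---|---|---|---|
| 2 | 93.8% | 100% | 100% | 96.0% | 0.50 |
| 4 | 87.5% | 100% | 100% | 92.3% | 0.125 |
| 5 | 84.4% | 100% | 100% | 90.6% | 0.063 |
| 6 | 81.3% | 100% | 100% | 88.9% | 0.031 |
| 8 | 75.0% | 100% | 100% | 85.7% | 0.008 |

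**How far this depends on the assumptions.**
- If the k foci sit among the planned 48 positives instead, k = 6 gives PET specificity 32/38 = 84.2% under 5.4, and CT sensitivity 42/48 = 87.5% under 5.2.
- With three other PET false positives, k = 6 gives 23/32 = 71.9% against 23/26 = 88.5%, a gap of 16.6 points rather than 18.8.
- One discordant lesion the other way (6 against 1) gives p = 2 × (1 + 7)/2^7 = 0.125. This applies to sensitivity (one CT-only true lesion) and to specificity (one CT-only false positive) alike.
- The p-values treat lesions as independent. If the six foci came from three patients, a patient-level sign test gives 2 × 0.5^3 = 0.25.

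**Patient level.** Sensitivity by patient changes only for a patient whose sole lesion is such a focus.

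**The case against.** Only 5.4 uses the term gold standard, and it sets out a two-tier hierarchy. Section 5.2 is about reading: counting lesions, site categories, imaging parameters, blinded readers and a consensus read. In that setting both the PET-only sentence and the small-node sentence can simply tell readers what to call positive. Section 5.1.3 also treats CT/MRI as the confirming test. On this view there is no conflict.

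That reading is fair, and it rules out a stronger inference that a reader might draw: that the plan has adopted PET as its own reference standard and will be biased towards PET. The documents do not establish this. But they do not exclude it either. The PET-only sentence comes straight after the CT/MRI confirmation rule and reads equally well as an exception to it, and the labels are worded as disease status rather than as a scan result. Section 5.1.3 does not say what happens when confirmation fails.

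Two further cautions stand. The 24-hour call is a safety check; it shows that the protocol schedules no follow-up imaging, not that routine follow-up CT/MRI will be absent. And k is unknown, so no particular bias can be claimed. Finally, 5.4 alone is not neutral: its second tier uses CT or MRI to judge CT.

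**Conclusion.** The point holds as an unstated choice between two readings, not as proof that the wrong one was made. Lesion sensitivity, lesion specificity and the McNemar comparisons depend on it; patient-level sensitivity hardly does. The defect exists for any k of at least one, but its size cannot be derived from the documents. At the illustrative k = 6 (7.5% of planned lesions), PET specificity is 81% or 100% and CT sensitivity is 100% or 89%.

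It would be tempting to conclude that the choice decides statistical significance, since p = 0.031 changes sides. That should not be relied on: neither p-value survives a single discordant lesion in the other direction, none is below 0.05 at k of 5 or fewer, and clustering is ignored. The stated precision figures are not in error on their own inputs. Because the truth rule defines the primary estimates, it should be settled before any lesion is classified.

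**What to change.** 1. In 5.2, record PET-only foci and avid nodes under 1 cm as PET-positive: a read result, not true NET.
2. In 5.4, state that lesion truth comes only from pathology, otherwise from initial and follow-up CT/MRI, independent of the study PET.
3. Report the number of PET-only foci without pathology, and how many of them have no follow-up CT/MRI or lay outside the diagnostic CT/MRI field.
4. As a sensitivity analysis, repeat lesion sensitivity, specificity and the McNemar comparisons with these foci counted all true and then all false. Treat CT-only lesions without pathology the same way, so that neither method is favoured.

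The cost is wording in two sections and a repeat of the lesion analysis under alternative labels, with no extra scans, readers or patients. The downside is a wider and possibly less favourable range of accuracy estimates.

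### No PET reader is stated to be blind to the reference standard, and the consensus reader is given clinical information, so PET sensitivity may be biased upward

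*Combined protocol and SAP*

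**What the plan says.** **Reading (protocol 5.2).** Each 68Ga-DOTATOC scan "will be read by two independent, board certified nuclear medicine physicians blinded to the results of other scan". A third physician "will then review both the results (independent reviews) and clinical information to reach to a consensus". The section defines neither the other scan nor the clinical information.

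**Reporting (5.1.3).** On abnormal uptake the section says: "These areas of abnormal uptake will be compared with any prior cross-sectional imaging (CT or MRI) within 12 weeks to confirm the presence of lesions".

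**Reference standard (5.4 Statistical Analysis).** First choice: "Results from pathology reports available from previous biopsy or surgical specimens will be considered the gold standard". Fallback, given the same status (quote cut one word short): "In the absence of pathology reports, initial and follow up diagnostic CT or MRI scan following nonsurgical therapy including chemotherapy will be considered the gold".

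**What exists before the PET read (3.0).** Patients may enter with histologically confirmed disease (3.5). Criterion 3.6 requires: "A diagnostic CT or MRI of the tumour region or suspected area within the previous 4-6 months prior to dosing day is available".

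**Analysis (5.4 Statistical Analysis).** Sensitivity, specificity, kappa and McNemar's test are planned. The section does not say whether the consensus read or the two independent reads enter them.

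**The concern.** An accuracy estimate is meant to show what the index test finds without help from the answer. A PET reader who knows that biopsy proved a pancreatic tumour, or that CT showed a liver lesion, is more likely to call faint uptake at that site. The call then counts as a true positive against the same biopsy or CT. This is review bias, and its usual direction is toward higher sensitivity and closer agreement with the reference.

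The primary goal of the trial is diagnostic accuracy, so the main result is at stake. The planned confidence interval does not cover this bias, and more patients would not reduce it. The unnamed read adds a second problem, because the choice between the independent reads and the informed consensus could be made after the results are known.

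**Working it through.** **1. Is the reference information available at the time of the read?**

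| Reference component (5.4) | Exists before the PET read? | Withheld from any reader? |
|---|---|---|
| Pathology from earlier biopsy or surgery | Yes, where it was done | Not stated |
| Initial CT/MRI | Yes, required by 3.6 | Not stated; 5.1.3 compares uptake with earlier CT/MRI up to 12 weeks old |
| Follow-up CT/MRI after therapy | Normally not; the consensus has no stated timing | Not stated |

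The first two rows carry the point. A site could give the third reader the pathology report and still comply with 5.2. For the first two readers, blinding to another scan might cover CT/MRI, but the text does not say so, and pathology is not a scan.

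**2. The plan's own precision figures.** Inputs from 5.4 Justification of Sample Size: 40 patients and 80 lesions, 60% positive, so 48 positive and 32 negative. Half-width = 1.96 × √(p(1−p)/n) at p = 0.5, with no clustering:

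- lesion sensitivity, n = 48: 14.1% (plan: 14%)
- lesion specificity, n = 32: 17.3% (plan: 17%)
- patient sensitivity, n = 40: 15.5% (plan: 15%)

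The figures reproduce to within about half a point. They describe sampling error only and say nothing about how the reads are made. At a sensitivity of 90% the half-width is narrower: 8.5% for 48 lesions and 9.3% for 40 patients.

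**3. Effect of one changed read.** One patient moved from miss to hit adds 1/40 = 2.5 points. One lesion adds 1/48 = 2.1 points.

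**4. Illustration.** Let s be the blinded sensitivity and f the share of blinded misses that become hits once the reader is informed. Informed sensitivity = s + f(1−s), so the gain is f(1−s). The documents give neither s for this trial nor f. Two cited studies in section 2.3 supply patient-level values for s; f = 0.5 is assumed.

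- DOTATOC study (69 true positives, 2 false negatives): s = 69/71 = 97.2%. Expected misses among 40 are 40 × 2/71 = 1.1. Gain = 0.5 × 2/71 = 1.4 points.
- DOTATATE study (41 of 47 positive): s = 41/47 = 87.2%. Expected misses among 40 are 40 × 6/47 = 5.1. Gain = 0.5 × 6/47 = 6.4 points, to 93.6%.

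The first study used this trial's tracer. The second used another tracer, in patients whose In-111 scans were negative or equivocal. Neither is a forecast.

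**5. Wider range, all values assumed.** Informed sensitivity by s and f:

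| s | f = 0 | f = 0.10 | f = 0.25 | f = 0.50 |
|---|---|---|---|---|
| 0.70 | 0.70 | 0.73 | 0.775 | 0.85 |
| 0.80 | 0.80 | 0.82 | 0.85 | 0.90 |
| 0.90 | 0.90 | 0.91 | 0.925 | 0.95 |

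The gain runs from 0 to 15 points. The largest corresponds to about 7 of 48 lesions (48 × 0.5 × 0.30 = 7.2).

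**The case against.** The best defence is that the text is silent rather than wrong. Four stronger conclusions are tempting, and the documents support none of them.

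- *The consensus reader sees pathology and CT/MRI.* A reader might infer this, since clinical information on an oncology patient ordinarily includes both. The term is undefined, so the supportable statement is that nothing withholds them. Follow-up CT/MRI would normally not yet exist.
- *The blinding of the first two readers is undone by the third.* That credits the first two with blinding to the reference standard, which 5.2 does not state. Blinding to the reference is not established at any step, so restricting the third reader alone would not be enough.
- *The informed consensus is the scored result, so sensitivity is inflated.* The consensus is the only single final PET read that the plan produces, but 5.4 does not name it as the one analysed. An informed reader may change no calls, or may withdraw some.
- *McNemar's test is tilted toward PET.* The three-reader process is stated only for 68Ga-DOTATOC, and 5.2 applies the same imaging parameters to In-111 images without mentioning readers. That is silence about the conventional reads; it does not show that they are single or unblinded. There is also an opposing bias: where pathology is absent, CT or MRI is the gold standard, so diagnostic CT is scored partly against itself. The net direction cannot be settled.

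It is also fair to say that informed reading reflects clinical practice. That is a reason to report it, but not to make it the primary result when it is scored against the same information.

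The gap in blinding remains. A reading rule that permits access to the reference standard is a design weakness even if some sites would read more strictly.

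**Conclusion.** The point holds in a limited form. The plan does not keep the PET read blind to the pathology and initial CT/MRI it is scored against, and it does not name the read to be analysed. PET sensitivity may therefore be biased upward.

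The size is unknown. With half of blinded misses converted, the two cited studies give 1.4 and 6.4 points; with none converted there is no bias. Both figures lie inside the planned ±15%, but that is a worst-case width, and 6.4 points is not small beside the 9.3% half-width that 40 patients give at 90% sensitivity. The conclusion assumes that the informed read could be the one scored and that reference findings could reach a reader. The text leaves both open. The plan should be changed before any scan is read.

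Section 5.2 also says of foci seen on PET but not on morphologic images that "such lesion/s will be considered positive NET". That is a separate bias, which blinded reading would not remove.

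**What to change.** Amend 5.2, 5.1.3 and 5.4 Statistical Analysis, and repeat the wording in the reading instructions:

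1. Name the blinded PET read as the index test for the primary sensitivity, specificity, kappa and McNemar analyses, and say how the blinded reads are combined into it.
2. Withhold pathology, separate diagnostic CT/MRI and their reports, In-111 results and follow-up from all three readers until the read is locked and dated. The low-dose CT acquired with the PET is part of the index test and stays available.
3. Do the 5.1.3 comparison with earlier CT/MRI, and the 5.2 confirmation of lesions by cross-sectional imaging, only after lock. The small-node rule in 5.2 depends on size on CT or MRI, so state whether it uses the low-dose CT or is applied after lock.
4. Define the clinical information, and report the clinically informed consensus as a secondary result with each blinded reader's result beside it.

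This is a cheap improvement: the same three readers, no extra scans, and no change to the 40 patients or the planned precision. The downside is that PET sensitivity may look slightly lower than in clinical use; the secondary informed result shows that difference.
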